3.0 Intervention to be studied

Babystrong device: For this proposal we will use two potential prototypes for the BabyStrong system: 1) an FDA cleared taVNS unit, with Neolead® electrode in front of the tragus and

custom ear electrode for infant sized ears at the inner tragus or cymba conchae, wired trigger control of stimulation with a trigger button or direct input in the taVNS unit; 2) an FDA cleared taVNS unit, stimulating on the vagus stimulation channel, with custom electrode at the cymba conchae with return to the mastoid and direct wired control of stimulation vis the taVNS unit.

These two different TENS units are FDA-cleared for clinical research and will serve as the electronic pulse generators, manufactured in compliance with ISO 13485 in a Medical Device Single Audit Certified (MDSAP) certified and FDA registered facilities. They both possess constant impedance readings to indicate loss of electrode contact.

Ear Electrodes: We will use a custom 3-D printed ear electrode with carbon conductive material for the inner tragus electrode, and a standard Micro Neolead® hydrogel return electrode at the outer tragus (used on neonates in the NICU), and wired connection to the EPG, for the inner tragus or cymba conchae to outer tragus group. For the second prototype, the ear electrode with be used with stimulation at the cymba conchae and return to the mastoid.

Operation of the EPG will be performed as follows, using the same protocol as in our pilot trial:

- a. To determine the PT, we will press the increase button in 0.1mA increments until we observe for infant detection of the tingling, with shoulder shrug or facial expression change, indicating the perceptual threshold (PT).
- b. Once PT is determined, the current will be delivered at 0.1mA less than PT. Parameters can be reset for each session or for infant possibly sensing the tingling, by pressing *pause* button and pushing the increase or decrease button.

FDA designation: We recently received Breakthrough Device designation from the FDA for the BabyStrong device. Our infant taVNS feeding data, ¹⁶⁻¹⁷ our early FDA breakthrough device development for young infants, and other studies indicating positive results of taVNS paired with motor learning in adults, ²⁶⁻³² support study of this neuromodulatory technique in infants with significant motor deficits of hemiplegia after perinatally acquired brain injury.

Non-Significant Risk device designation: We have IRB approval for two pilot studies in preterm and term infants using the custom modified devices and taVNS study procedures proposed in this application. The taVNS systems have non-significant risk device designations from MUSC's IRB in our pilot trials.

Proposed Trial of BabyStrong taVNS feeding system

We will conduct a small-scale safety and efficacy study of several versions of the prototype BabyStrong portable taVNS feeding system. We will test the prototypes using a maximum of active (n=10) or sham (n=10) taVNS in infants with twice daily A/B treatment for 10days, with crossover to B/A treatment if there is no progress with feeds. Care providers, study personnel and parents will be blinded to treatment assignment.

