8.0 Recruitment Methods

The clinical team will refer parents for participation if their infants are failing oral feeds and are approaching G-tube placement per unit guidelines. [name] will also screen EPIC (chart review) for infants in the nursery with known brain injury that may have poor feeding, such as perinatal arterial stroke, HIE, severe IVH, PVL or cerebellar infarct, regardless of sex or race.

After screening and consent we will randomize infants to receive either active or sham taVNS. The assignment will be blinded to care providers, investigators and parents. Recruitment of 20 infants in 9 months will require enrolling 2-3 infants/mo. In the pilot study we frequently were unable to accommodate all requests, due to equipment limitations. With several BabyStrong units, we anticipate no problems completing enrollment.

Infants of all ethnicities and racial categories will be accepted into this study protocol. No preference will be given based on race, gender or ethnicity. Young infants who had perinatal complications leading to perinatally acquired brain injury are **vulnerable** populations and are the target of this proposal.

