10.0 Study Design / Methods

Phase I Protocol:

MRI scan: We will obtain an unsedated diffusion scan on our clinical Siemens 3T MRI prior to initiating treatment and at the end of the 10day treatment period for all infants (2 scans if no cross over) and again at the end of the 7d alternative treatment if applicable (3 total scans for those infants who receive cross-over treatment).

Active taVNS treatment: The study team will determine the PT daily, then the nurse, therapist or parent will deliver active taVNS at 0.1mA less than the PT, with one of the BabyStrong prototypes during 2 bottle feeds a day. We will record the HR, NIPS scores by nurses before, during taVNS, and whether current is decreased for NIPS.

Sham treatment will use one of the BabyStrong prototypes via on/off switch as for active taVNS. We will test the PT with active stimulation, as care providers expect a brief HR decrease. We will then program a sham setting on the TENS unit to deliver no current after the PT is determined. We will check integrity of sham protocol by de-identified survey of nurses and parents, asking which treatment condition they thought the infant had received.

Cross—over treatment: If progress in daily oral feeding volumes is <4ml/kg/d (based on response rate in pilot trial) after 10 days with either treatment A or B, we will offer cross-over to the alternate treatment. If no further progress is noted after 7 days on alternate treatment, parents and the clinical team will arrange for a G- tube. Any parent can decide to withdraw the baby from the study at any time.

Breast feeding will be allowed, and we can stimulate with breast feeding, if the parent desires. We will offer bottle supplementation ad lib post-BF, and count this as a full volume feed, per standard clinical practice.

Training for safety using a variety of feeders: All individuals, including pediatric speech and languagepathologist (SLP), OT, nurses and parents who feed infants using this device will undergo training on the device operation by study staff. Research staff will supervise all feeders during the taVNS feedings. All feeds will be done in the NICU

The alternative treatment is the usual and customary occupational or speech therapy services which the infant has already been receiving, or to get a G-tube.

Safety measures:

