We will monitor for and mitigate following risks are present with this study: Risk of skin irritation, risk of discomfort, risk of bradycardia, and risk of loss of confidentiality.: We will monitor for bradycardia (HR<80bpm), as all infants are on cardiorespiratory monitoring in the NICU; We will monitor for skin irritation at left ear daily.

Risk of skin irritation: we will monitor the skin on the inner aspect of the left ear before and after each session, and will switch to the right ear if redness is present, and decrease the stimulation if redness persists.

Risk of discomfort: We will protect against the risk of discomfort by close monitoring. We will measure infant discomfort using the NICU standard scoring tool, the NIPS (Neonatal Infant Pain Scale) recording at the beginning, middle and end of taVNS session. If we observe a sustained >3 point Δ NIPS, we will decrease current by 0.1mA until discomfort resolves.

Risk of loss of confidentiality: We will check the infant's medical records to gather the following information: gestational age at birth, ventilator support, head ultrasound and MRI results, bottle feeding, infection, neonatal condition during labor and delivery, infant's treatments and conditions, and developmental progress. The neonatal chart by necessity contains some

information about mother during her pregnancy, and labor and delivery. We will collect mother's information if it is pertinent to infant's condition, including chorioamnionitis, abruption, fetal movement, bleeding, preterm labor, infections, medications,

We will assign study numbers to each participant, keep CRF and consent forms in locked offices. Database files with names and contact information will be password protected and stored on the MUSC Pediatric server. All other data files related to this study will be identified by participant number only, without link to standard identifiers. We will publish the aggregate data only.

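### Study personnel and investigators are said to be blinded, yet someone on the team must set the device to no current for sham, and no coded setting or unblinded operator is described

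*Protocol*

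**What the plan says.** Three places in the protocol state who is blinded, and the lists differ.

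- Section 3.0 (Proposed Trial): "Care providers, study personnel and parents will be blinded to treatment assignment".
- Section 8.0: "The assignment will be blinded to care providers, investigators and parents".
- Section 1.0, Aim 2, lists only care providers and parents. This is narrower and does not contradict the other two.

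The procedure is in sections 3.0 and 10.0.

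- Threshold testing: "The study team will determine the PT daily". Sham infants also receive active current for this test.
- Active setting: "Once PT is determined, the current will be delivered at 0.1mA less than PT".
- Sham setting: "We will then program a sham setting on the TENS unit to deliver no current after the PT is determined".
- Later changes: "Parameters can be reset for each session or for infant possibly sensing the tingling" (section 3.0), and, for a sustained rise in the pain score, "we will decrease current by 0.1mA until discomfort resolves" (section 10.0, Safety measures).
- Crossover after too little progress: "we will offer cross-over to the alternate treatment".

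Section 10.0 has research staff supervise all feeders during stimulated feeds. Section 13.0 has the principal investigator, a co-investigator or the research assistant report perceived adverse events. The blinding check in section 10.0 is a survey of nurses and parents only.

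**The concern.** The blinding of study personnel and investigators is stated without exception, but the described procedure needs a person who knows whether the unit delivers current. If a report repeats sections 3.0 and 8.0, it will claim a level of blinding that the trial did not have as described. This matters because the study is meant to supply clinical data for an FDA application and to prepare a pivotal trial (section 1.0).

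Some staff tasks also involve judgement, such as supervising feeds and deciding what counts as a perceived adverse event. Nothing in the text keeps the person who sets the device out of those tasks. Because the survey covers only nurses and parents, it would not show whether staff blinding held.

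**Working it through.** No sample-size, power or error-rate calculation bears on this point, and the protocol gives no figure to reproduce. The check compares the blinding statements with the device procedure.

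1. **Who is said to be blinded.** Study personnel (section 3.0) and investigators (section 8.0), with no exception in either place.

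2. **What must be set after threshold testing.** Active: PT − 0.1 mA (sections 3.0 and 10.0). Sham: 0 mA (section 10.0). These are different settings, and choosing between them requires knowing the arm. An active setting reveals the arm as surely as a no-current setting does, so infants in both arms are affected.

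3. **Who sets it.** The sham sentence says only 'we'. The paragraph before it gives threshold testing to the study team, while the nurse, therapist or parent delivers the treatment. Programming follows directly on threshold testing, so study staff is the natural reading. If care providers set the unit instead, the blinding claim would fail for them.

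4. **Whether anything hides the arm from that person.** Treatments are labelled A and B in sections 1.0, 3.0 and 10.0, but the labels are not linked to a coded device setting or to a holder of the code. Section 13.0 names two people who oversee use of the stimulation system, without making either one an unblinded operator. Section 3.0 describes manual operation with pause, increase and decrease buttons.

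5. **How often it arises.** The threshold is found daily, parameters may be reset at each session, and current may be lowered for discomfort. Under sham there is no current to lower, and the text does not say who carries out that step or how the arm is hidden from them. At crossover the new setting reveals the alternate arm.

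6. **Extent.** 10 active + 10 sham = 20 infants at most (sections 3.0 and 6.0). This is the enrolment ceiling. It counts the infants whose setting reveals the arm and does not measure bias.

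7. **What is not affected.** Threshold testing itself does not unblind, because both arms receive active current for it. Nothing shows that parents or care providers learn the arm.

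**The case against.** The strongest reply is that the text leaves a mechanism undescribed and does not show blinding to fail. On this view:

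- 'We' is used loosely throughout the protocol.
- The A/B labels suggest coded allocation, and the sham setting could be a stored program that most staff select without knowing its content.
- At most one operator is unblinded.
- Pressing a decrease button does not in itself reveal an arm, and the text does not say what the unit displays under sham.
- Full feeds, bradycardia and the crossover trigger are numeric, nurses score NIPS, and sections 4.0 and 12.0 disclaim power.
- In a single unit with at most 20 infants, strict separation of roles may be more than the problem warrants.

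Much of this stands as a limit on the consequence. The protocol does not say that the operator also supervises feeds or reports adverse events, and the adjustment steps are supporting evidence only. It does not rescue the claim. A stored program still has to be set by someone on the staff, and the protocol describes programming no current in plain terms. If one unblinded operator was always intended, the unqualified references to study personnel and investigators are wrong for that person and need correcting. Who sets the device and who is blinded are matters of trial conduct, so a separate analysis plan would not be expected to settle them.

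**Conclusion.** The concern holds. The blinding of study personnel and investigators, as sections 3.0 and 8.0 state it, is not delivered by the procedure in section 10.0. It fails for at least the person who sets the device, potentially for all infants (up to 20) and again at crossover. This rests on reading 'we' in the sham paragraph as study staff and on the absence of any coded setting or designated operator in the protocol. No size or direction of bias can be derived, overlap of roles is possible but not stated, and the blinding of parents and care providers stands. The point should be fixed because the statement is wrong as written and cheap to correct. It does not threaten the study's descriptive aims.

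**What to change.** Reconcile sections 3.0 and 8.0 with section 10.0 in one of two ways.

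1. **Keep staff blinding, with a named exception.** Designate an unblinded member of the existing team to set and adjust the device. For those infants, that person does not supervise feeds, report perceived adverse events or judge the crossover criterion. If the units allow it, coded A/B settings would serve instead. The cost is wording, plus cover by another team member for those tasks.

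2. **Narrow the claim.** State that care providers and parents are blinded, as Aim 2 does, and drop study personnel and investigators from the list. This needs no extra staff but gives up the claim of staff blinding.

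Neither option changes a current level, a discomfort rule or the crossover criterion.

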4.0 Study Endpoints

Primary outcome: We will compare the numbers of infants who attain full oral feeds (> or = 130ml/kg/d with weight gain). We do not anticipate having power to compare any outcome with valid statistical measures.

Primary Safety Outcomes: Bradycardia (HR<80bpm for 5 seconds); discomfort measured by Neonatal andInfant Pain scale (NIPS) >3 point change, equivalent to pain with heelstick for blood drawing ^{34, 35}.

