Aim 2. Conduct a small-scale safety and efficacy study of the BabyStrong portable taVNS feeding system. We will test the prototype BabyStrong feeding system using active (n=10) and sham (n=10) taVNS ininfants with twice daily A or B treatment for 10 days, with cross over to B/A treatment if there is no progress with feeds. The treatment assignment will be blinded to care providers and parents. We will compare daily po volumes over 10 days prior and the 10 days of treatment. Safety measures will be bradycardia and discomfort.

Criteria for success of BabyStrong feeding system: No sustained increase in discomfort scores or bradycardia; attainment of full oral feeds in 50% ofinfants.

Success of Phase I aims will position us well for Phase II and a pivotal RCT clinical trial with cross-over design, to determine if the BabyStrong system allows preterm and term infants with feeding failure to be discharged sooner and avoid costly complications as well as prolonged hospital stays. If successful, the BabyStrong device could have significant impact on the infants, their families, and hospital costs, as well as set the stage for greater use of taVNS targeted plasticity in neurodevelopmental disorders like cerebral palsy.

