6.0 Number of Subjects

We will enroll up to 20 infants.

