12.0 Data Management

Power Analysis: We do not anticipate being powered to determine efficacy in feeding response rate, or test for A/B or B/A effects

Keeping Data Confidential: We will assign study numbers to each participant, keep CRF and consent forms in locked offices. Database files with names and contact information will be password protected and stored on the MUSC Pediatric server. All other data files related to this study will be identified by participant number only, without link to standard identifiers. We will publish the aggregate data only.

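### The protocol ties low power to a lack of valid statistical measures for every outcome, and words the oral-volume comparison as before against during treatment, with no stated use of the randomised sham arm

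*Protocol*

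**What the plan says.** Section 4.0 makes the primary outcome a comparison of the numbers of infants attaining full oral feeds, defined as at least 130 ml/kg/d with weight gain. It gives no time point. The next sentence is: "We do not anticipate having power to compare any outcome with valid statistical measures".

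Section 12.0, under Power Analysis, returns to the subject in terms of power alone: "We do not anticipate being powered to determine efficacy in feeding response rate, or test for A/B or B/A effects". It gives no significance level, effect size or power figure.

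Aim 2 in section 1.0 adds a second feeding measure: "We will compare daily po volumes over 10 days prior and the 10 days of treatment". No contrast between arms is stated for it.

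The design would support such a contrast. Section 8.0 says "we will randomize infants to receive either active or sham taVNS", with assignment blinded, and section 3.0 sets the size at "a maximum of active (n=10) or sham (n=10) taVNS". Section 10.0 offers the alternate treatment after 10 days if daily oral volume has progressed by less than 4 ml/kg/d, so the arms are cleanly randomised only through day 10.

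**The concern.** Two statements need correcting.

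First, section 4.0 puts power and validity into one sentence and applies it to any outcome. They are different properties. A small trial can give an estimate and an interval with the stated error rate; the interval is simply wide. Section 12.0 makes the power point without bringing in validity, so section 4.0 goes further than the protocol's own power statement.

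Second, the volume comparison is framed as each infant's 10 days before against the 10 days of treatment. These infants are still learning to feed and continue to grow and practise. A rise in volume from one period to the next is expected to some degree without any stimulation. The sham arm measures that rise, but the wording makes no use of it.

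Aim 2 is meant to inform Phase II and a pivotal trial. A before-during rise read as a treatment effect would mislead that planning, and the trial's randomised information on volume would go unused.

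**Working it through.** **Inputs from the protocol.** At most 10 active and 10 sham (section 3.0); binary primary outcome (section 4.0); daily oral volume for 10 days before and 10 days on treatment (section 1.0, Aim 2); cross-over offered after day 10 (section 10.0).

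**Assumed, because the protocol gives no figure.** Two-sided 5% level; 50% full feeds on active (close to the 52% pilot figure in section 1.0); sham rate 0-40%; correlation *r* between prior and on-treatment mean volume of 0.5-0.7; effects in SD units; no dropout. There is no stated power figure to reproduce, only the qualitative statement that power is low.

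**1. Is the low-power statement right?** Power of Fisher's test is the sum, over all pairs (a, b) with two-sided p ≤ 0.05, of Bin(a; 10, p₁) × Bin(b; 10, p₂). With p₁ = 0.50:

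| Sham rate | 0% | 5% | 10% | 20% | 30% | 40% |
|---|---|---|---|---|---|---|
| Power | 0.623 | 0.431 | 0.295 | 0.132 | 0.055 | 0.022 |

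Yes. At 50% against 20%, 80% power needs 39 per arm by the normal approximation, or 45 with continuity correction.

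**2. Are there valid measures at 10 against 10?** The largest true type I error of two-sided Fisher at nominal 0.05 is 0.013. For a baseline-adjusted (ANCOVA) comparison, 20,000 simulated trials at each of r = 0.5 and 0.7 gave type I error of 0.049-0.052 with normal errors and 0.043-0.046 with skewed errors. Both hold their level.

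**3. What would an interval look like?** Take 5/10 against 2/10 as an illustration. The Wilson limits are 0.237-0.763 and 0.057-0.510. Newcombe's score-based interval for the difference of 0.30 is:

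- lower: 0.30 − √[(0.500 − 0.237)² + (0.510 − 0.200)²] = 0.30 − 0.407 = −0.107
- upper: 0.30 + √[(0.763 − 0.500)² + (0.200 − 0.057)²] = 0.30 + 0.300 = 0.600

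That is −11 to +60 points. The exact unconditional interval is about −14 to +67. Both are wide, and they are valid.

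**4. What does the before-during contrast estimate?** Let m be the average rise without stimulation and t the effect of stimulation. The before-during change is m + t in the active arm and m in the sham arm. Pooled over equal arms it is m + t/2. None of these is t. The between-arm difference is (m + t) − m = t.

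**5. What does baseline adjustment add?** Adjustment multiplies the residual variance by 1 − r². For a difference of d SD with 10 per arm, the noncentrality is d / [√(1 − r²) × √(2/10)]. With d = 1:

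| Analysis | Noncentrality | df | Power | Difference detectable with 80% power |
|---|---|---|---|---|
| Unadjusted | 1/0.447 = 2.24 | 18 | 0.562 | 1.33 SD |
| Adjusted, r = 0.5 | 2.24/0.866 = 2.58 | 17 | 0.682 | 1.15 SD |
| Adjusted, r = 0.7 | 2.24/0.714 = 3.13 | 17 | 0.839 | 0.95 SD |

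**The case against.** The strongest reply is that section 4.0 speaks of lacking power, and section 12.0 confirms that sense. On this reading the sentence means only that the trial is too small for a useful hypothesis test, which is true. This stands in part. A reader might infer that the protocol declares every comparison invalid or forbids intervals. It does neither. What remains is that the sentence links validity to power and reaches every outcome.

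A reader might also infer that the trial would report nothing but counts. The documents do not support that: Aim 2 plans a volume comparison as well, and an analysis plan that is not shown may name intervals, models and upper limits for safety events. Their absence from the protocol is not a fault.

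Aim 2 does not exclude a comparison between arms, and its sentence stands in the paragraph that sets out the active and sham groups. That is fair. But the two things it says will be compared are the two time periods.

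Finally, the gain in step 5 depends on an assumed correlation and a large effect. Section 10.0 counts a breast feed followed by ad lib supplementation as a full-volume feed, which adds measurement error, and volumes may level off as infants reach full feeds. These points limit the size of the gain. They do not affect step 4, which holds at any correlation.

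**Conclusion.** The point holds as a correction to two statements. Low power is correctly declared (about 13% for an assumed 50% against 20% at 10 per arm), but it implies imprecision, not a lack of valid measures. The volume comparison as worded estimates maturation plus treatment and makes no stated use of the sham arm. A first-period comparison between arms, adjusted for the baseline that the trial already plans to collect, targets the treatment effect and raises power for a 1 SD difference from 56% to about 68-84%.

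That range rests on an assumed correlation of 0.5-0.7, two filled arms and no dropout. Ten per arm is a maximum, so smaller arms would do worse. Even with adjustment, 80% power needs a difference of about 0.95-1.15 SD. The change does not make the trial adequately powered for the primary outcome.

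**What to change.** In section 4.0, replace the disclaimer with wording such as: *The trial is not powered for hypothesis tests. The active-sham difference in the proportion attaining full oral feeds in the first 10-day period, before any cross-over, will be reported as an estimate with an exact or score 95% interval.*

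In section 1.0, Aim 2, replace the volume sentence with wording such as: *Mean daily oral volume in the first 10-day treatment period will be compared between arms, adjusted for the mean of the 10 days before treatment, and reported with a 95% interval.* Within-infant changes can still be shown descriptively by arm.

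The change needs no extra infants or data: a few sentences and one short analysis. Its visible price is wide intervals. The report should also say how many feeds were breast feeds counted as full volume, since they blur the volume measure.
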